2.2 Rationale

Primary Aims. To examine: *i*) whether African Ancestry (%AF) is associated with decreased SWS duration and SWA; *ii*) the effects of race on longitudinal amyloid build-up and its interaction with baseline SWS duration and SWA in cognitively normal elderly; *iii*) the effects of race and its interaction with baseline SWA on longitudinal changes in global cognition, memory, executive function and a spatial navigational memory task. **Exploratory aim.** We will test whether loss of sleep-dependent spatial navigational memory at baseline is a predictor of cognitive decline at follow-up.

Rationale for ethnicity/nativity and clinical groups selection:

Multiethnic cohort studies provide better information about disease causation but they are expensive to design. We will focus on 150 African-American (AA) blacks since African or Caribbean-born are not equally admixed and inclusion of more ethnic groups would result in loss of power for Aim 1 and need for great increases in sample size. As a comparison group, we will include 60 matched non-Hispanic whites. Race will be represented both as binary (self-identified AA vs. self-identified white) and numeric (% of African ancestry). Irregular sleep-wake rhythms and extreme sleep durations may also increase AD risk⁶⁸⁻⁷⁰. The study will not formally test these sleep disorders, as these subjects are hard to recruit in community-based

CONFIDENTIAL

studies (often reluctant to participate in studies that monitor sleep) and the focus is on SWS. Insomnia will be allowed as long as total sleep time (TST) is between 5-9 hours based on actigraphy recordings and sleep logs performed at home.

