3.1 Primary Objective

Aim 1 will test if African ancestry (%AF) is associated with short SWS duration and poor SWA in older AAs. **Challenge:** AAs consistently spend less time in SWS than whites²³⁻³². Although SWS shows significant heritability, social stressors may moderate these differences. **Approach:** test whether %AF⁴⁰ is associated with SWS characteristics after controlling for psychosocial factors (*e.g.* stress related to ethnicity). **Outcome:** positive results would suggest that racial differences in SWS have genetic underpinnings.

Aim 2 will test the effect of race and its interaction with baseline short SWS duration/poor SWA on longitudinal amyloid deposition. **Challenge:** AAs spend less time in SWS²³⁻³², a sleep stage important for A β dynamics⁴¹⁻⁴³ that may confer protection against amyloid deposition⁴⁴. **Approach:** assess how race is associated with longitudinal PiB uptake and its interaction with short SWS duration and poor SWA, after controlling for: 1) medial prefrontal (mPFC) atrophy, TST, AHI4% and cerebrovascular damage (measured as white matter lesion [WML] volume and abnormal diffusion kurtosis imaging [DKI] indices); and, 2) psychosocial factors, health care behaviors and medical morbidity. **Outcome:** reduced SWS/SWA would become a novel risk factor for AD in African Americans (AAs).

Aim 3 will test the effect of race and baseline poor SWA on cognition. **Challenge:** race and poor sleep have been associated with cognitive impairment. However, most studies are confounded by the inclusion of OSA patients, subjective measurements of sleep, lack of valid cognitive assessments for AAs and inadequate enrollment of minorities. **Approach:** we will test for the association between race and longitudinal changes in global cognition, memory, executive function and a sleep-dependent spatial navigational memory task. In addition, we will test their interaction with baseline SWA, using a similar approach as in Aim 2. **Outcome:** positive results would emphasize the importance of health messages promoting good sleep hygiene among AA elderly.

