Each in-lab NPSG will record sleep as recommended by the AASM²²⁵ as described in our previous work¹⁵⁶. Electrode attachment will be performed between 8-9 PM. Subjects will be then asked to sit quietly and/or read until lights out at their habitual bedtime. NPSG N1 will be for habituation, N2 will be for data collection. Arousal index (AI), sleep staging, TST, sleep efficiency and wake after sleep onset (WASO) during NPSG will be scored by one trained technologist blinded to PET data using standard AASM criteria²²⁵. Participants will go home between N1-2 provided that they wear the actigraph with off-wrist detection, avoid naps or exercise and track their meals. SWS will be scored visually as: 1) TST in SWS in min. (SWS duration); and, 2) %TST spent in SWS (%SWS). SWS measurements will be measured in N2. In addition, we will include: 1) slow wave activity (SWA): absolute SWA (defined as power between 0.5-4.0 Hz during NREM), relative SWA (SWA divided by power across all 0.4-50 Hz). NREM cycles will be defined as stages NREM2-3 of \geq 15 min. terminated by REM or wakefulness of \geq 5 min. Delta power will be averaged relative to the number of epochs. 2) SWS continuity: bouts of SWS will be defined as the duration of consecutive 30 sec. epochs of sleep scored as SWS, terminated by one or more epochs scored as another stage as described in our previous work^{226;227}.

Sleep-dependent Neuropsychological Tests:

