9.1 Study Hypotheses

1. Hypothesis 1.1: poor SWS characteristics (short SWS duration, low %SWS, low relative SWA, low SWS continuity and high AI) at baseline will be associated with high %AF. Hypothesis 1.2: psychosocial factors (*e.g.* perceived discrimination) will partially moderate the above relationships.
2. Hypothesis 2.1: race will be associated with longitudinal increases in the annual rate of AD_{PiB}mask change. Hypothesis 2.2: the effect of race in terms of longitudinal increases in AD_{PiB}mask will be partially explained by poor relative SWA at baseline.
3. Hypothesis 3.1: race will be associated with longitudinal changes in global cognition, memory, executive function and sleep-dependent spatial navigational memory. Hypothesis 3.2: the association of race in terms of cognitive decline will be partially explained by poor relative SWA at baseline. Exploratory Hypothesis: absence of improvement in sleep dependent memory consolidation at baseline will be associated with longitudinal decreases in global cognition, memory and executive function.

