9.3 Statistical Methods

General considerations: we will incorporate standard techniques such as omnibus tests and appropriate adjustments to significance (α) levels (*e.g.*, Bonferroni correction) for *post-hoc* contrasts to control for multiple comparisons. Both selection and attrition biases might occur. Appropriate techniques (*e.g.*, Heckman 2-stage approach (GEE Probit Model)^{254;255} and Monte Carlo (EM algorithm)²⁵⁶ will be used to address biases or missing data. Attributes of those who withdrew to follow-up will be contrasted with completers to determine sources of attrition biases. Since only two time points will be analyzed, we will use linear regression models with the annual rate of amyloid change as dependent variable. Significance will be defined by $p < .05$ where p will be Bonferroni corrected when testing *post-hoc* contrasts.

- **Hypothesis (1)**: H1.1) for %AF associations, linear regression models, with each of SWS characteristics as the dependent variable, will be regressed on %AF controlling for age, sex, BMI, AHI, TST, sleep efficiency and WASO. H1.2) This model will test interaction by including the best SWS predictor as dependent variable, the psychosocial factor as a classification factor, %AF and the term created as the cross product of psychosocial factors and %AF.
- **Hypothesis 2-3 (H2-3)**: First we will calculate the associations between race and AD_{PiB}mask represented both as binary (AA *vs.* white) and numeric (%AF). Further analyses will use the representation (s) of race significantly associated with amyloid burden. Second, we will use hierarchical

CONFIDENTIAL

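### The single sleep scorer's stated blind covers PET but not race or ancestry, which leaves the hand-scored Aim 1 outcomes open to a race-related shift if African Americans and whites are pooled or compared

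*Combined protocol and SAP*

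**What the plan says.** Section 6.1 gives the arousal index (AI), sleep staging, total sleep time (TST), sleep efficiency and wake after sleep onset (WASO) from polysomnography to one person. They "will be scored by one trained technologist blinded to PET data using standard AASM criteria". The SWS measures follow from the same staging: "SWS will be scored visually as: 1) TST in SWS in min. (SWS duration); and, 2) %TST spent in SWS (%SWS". Continuity does too: "bouts of SWS will be defined as the duration of consecutive 30 sec. epochs of sleep scored as SWS". Relative slow wave activity (SWA) is a spectral measure.

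Section 9.1 states H1.1 as: "poor SWS characteristics (short SWS duration, low %SWS, low relative SWA, low SWS continuity and high AI) at baseline will be associated with high %AF". In Section 9.3 the H1.1 models are linear regressions "with each of SWS characteristics as the dependent variable, will be regressed on %AF", and no restriction to AAs is given. Section 3.1, however, words the aim as whether %AF "is associated with short SWS duration and poor SWA in older AAs". Section 2.2 adds: "Race will be represented both as binary (self-identified AA vs. self-identified white) and numeric (% of African ancestry".

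Two other statements bear on the point. Section 2.3.1 says that sleep data are coded and de-identified; the purpose given is confidentiality, and recording and analysis are both placed at the same sleep center. It also says that follow-up interviewers are blind to prior diagnosis, which does not concern the sleep scorer.

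**The concern.** Visual staging and arousal scoring involve judgment. The plan recognises this by naming a blind, but the blind it names guards the link between sleep and amyloid. PET is not a variable in Aim 1, where the exposure is ancestry.

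The expected direction is written into the protocol: Section 3.1 takes it as established that AAs have less SWS than whites. With one scorer, a tendency to score the groups differently would not average out over readers. It would line up with race and look like the hypothesised result, which Section 3.1 would read as evidence of a genetic basis. Adjustment may not remove it. The H1.1 covariates include TST, sleep efficiency and WASO and, if the polysomnographic values are used, these come from the same scorer.

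**Working it through.** **1. Which H1.1 outcomes depend on the scorer (Sections 6.1 and 9.1)**

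| H1.1 outcome | Source | Scorer's judgment |
|---|---|---|
| SWS duration | visual staging | direct |
| %SWS | visual staging | direct |
| SWS continuity | runs of epochs staged as SWS | direct |
| AI | arousal scoring | direct |
| Relative SWA | spectral power in NREM | only through the choice of NREM epochs |

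Four of the five depend on it directly.

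**2. Is H1.1 pooled or AA-only?** Section 9.2 claims 80% power at the 5% level for |r| = 0.20 and assumes complete data from 200 subjects. It does not state sidedness; two-sided is assumed here. With Fisher's z, power = Φ(atanh(r)·√(N − 3) − 1.96), and atanh(0.20) = 0.2027.

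- N = 200: 0.2027 × √197 − 1.96 = 0.886, power 81%.
- N = 210: 0.2027 × √207 − 1.96 = 0.957, power 83%.
- N = 150 (AAs only): 0.2027 × √147 − 1.96 = 0.498, power 69%.

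The stated figure fits the pooled sample and not the 150 AAs.

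**3. The plan's own race comparison.** Section 9.2 also claims 80% power to detect a mean SWS duration 28% higher in whites, with CVs of 90% (150 AAs) and 40% (60 whites). Set the AA mean to 1:

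- SE = √(0.90²/150 + (0.40 × 1.28)²/60) = √(0.00540 + 0.00437) = 0.0988.
- Power = Φ(0.28/0.0988 − 1.96) = Φ(0.873) = 81%.

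This reproduces.

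**4. Illustration of a scoring shift.** Keep the same CVs and group sizes, with no true difference and both means equal to 1:

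- SE = √(0.81/150 + 0.16/60) = √0.00807 = 0.0898.
- For a shift b between the races, two-sided error = Φ(b/SE − 1.96) + Φ(−b/SE − 1.96).

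| Assumed shift, share of mean SWS duration | b/SE | Two-sided error |
|---|---|---|
| 0% | 0 | 5.0% |
| 2% | 0.22 | 5.6% |
| 5% | 0.56 | 8.6% |
| 10% | 1.11 | 20% |

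The shifts are assumptions; the documents offer no value. The results belong to an unadjusted two-group comparison with unequal variances. They do not carry over to the adjusted %AF regression, which would need the distribution of %AF and its relation to the covariates.

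**The case against.** The strongest reply is that the plan is silent on this, which is different from saying that the scorer is unmasked. A reader might infer that the technologist knows each participant's race, perhaps from attending the night or watching video. The documents do not support that. They do not say that the scoring technologist runs the nights, and they never mention video. Sleep data are coded (Section 2.3.1), and the Mount Sinai teams process them by logging into NYU drives (Section 12.1), which is consistent with scoring from files. This stands: the supportable statement is that masking to race is not stated. Coding for confidentiality does not, however, establish that race is hidden from the scorer.

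Second, the H1.1 exposure is genotype-derived %AF, which a scorer cannot see. In an AA-only analysis all participants share the same self-identified race, so knowing it gives little basis for a shift that tracks %AF. This also stands, and it makes the point conditional on pooling or on a direct race comparison. Section 9.2 powers such a comparison, although Sections 9.1 and 9.3 list no test for it.

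Third, a reader might extend the concern to Aim 2 or to masking of visit. Neither goes far. In Aim 2 the outcome is PET change, the lead sleep predictor is spectral, and the PET blind is the relevant one. It has a purpose even though the baseline scan follows both sleep nights, because scoring may take place after the scan. Visit matters little: the hypotheses use baseline sleep, and change in sleep appears only in a post-hoc analysis.

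**Conclusion.** The gap is real but limited. The only blind stated for the one sleep scorer is to PET, while four of the five H1.1 outcomes are hand-scored and the exposure is ancestry. It matters if H1.1 pools AAs and whites, as the power figure implies (81% at N = 200 against 69% at N = 150), or if SWS duration is compared by race. It matters little in an AA-only analysis.

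The documents do not show that the scorer knows race or that any shift will occur. It would be wrong to read the 20% as the expected false-positive rate of Aim 1: it is the result of an assumed 10% shift in an unadjusted comparison, and a 2% shift barely moves the error. The case for acting rests on how cheaply the route can be closed.

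**What to change.** In Section 6.1, extend the blind so that the scorer is blinded to self-identified race, %AF and PET data, and scores from files under a random recording ID that carry no demographic fields or video, with AA and white recordings in mixed order. Masking of visit (baseline or 30-month) can be added through the same relabelling, but it serves only the post-hoc analysis of sleep change. It would also help if Section 9.3 said whether H1.1 is fitted in AAs only or in the pooled sample, since that decides how much the point matters.

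The cost is a relabelling step on the shared drive that already holds the sleep data, and the loss of any video during research scoring. The clinical read by a sleep physician (Section 12) is unaffected. No second scorer, extra visit or change in sample size is needed. If the coded files already hide race, the amendment only records existing practice.

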Self-identified AA and whites will be balanced by sex, age, BMI, income and education, and will live in the same NYC zip codes. Brooklyn will be the area of recruitment as it is the most ethnically diverse and largest most concentrated black population in the US -more than 900,000 blacks living in a 4-mile square area-. The sample will include self-identified African-American (AA) blacks and non-Hispanic whites. As described in our published methods^{158;166}, enrollment sites will include advertisements and collaborations with black-owned barbershops, beauty salons and churches that were part of our previous community studies in Brooklyn and other NYC boroughs. All advertisements and recruitment materials will be submitted for IRB approval prior to use. In addition, we will perform culturally-relevant educational events in senior centers and church health fairs. Recruitment will be implemented in consultation with a Community Activist ([name]) and a Community Advisory Board (CAB) that has been created for this cohort. It will include community stakeholders with whom we have long-standing relationships and consist of: black community leaders serving as Directors of Community-based organizations (CBOs) and members of the Brooklyn chapter of *CaringKind*. The CAB will comprise 8 members and will meet with the PIs and [name], who will be one of the lead members of the community advisory board every 2 months during year 1 and every 3 months thereafter. Once the award is made, it will discuss project goals, review recruitment strategies, refer individuals for participation and suggest new recruitment sites that might not have been available previously. Our success in assessing sleep in AAs is attributable to our sustained engagement efforts at the community level and help from former CABs.

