On NPSG N2, participants will be trained in our published 3-D virtual maze spatial navigational test (see Figure 10)^{141;156}. Navigational memory represents a good model to study the effects of sleep-dependent memory consolidation. Rodent studies show that patterns of firing in hippocampal place cells during wake are replayed both in REM²²⁸ and NREM²²⁹ sleep. Behaviorally, sharp-wave ripple suppression impairs performance on a radial arm maze,²³⁰ while REM suppression impairs memory in the radial arm maze²³¹ and in the Morris water maze²³². In humans, overnight sleep enhances virtual maze navigation performance^{233;234}, while we have shown that maze completion time (CT) is attenuated after REM disruption¹⁷⁶ and is correlated with SWA in elderly subjects¹⁸⁸. Subjects will experience two different mazes at baseline and at the 2.5-year follow-up, and mazes will be counterbalanced across subjects for which maze is experienced first. Both mazes have been designed such that optimal CT is equivalent assuming perfect knowledge of the maze layout. Maze performance will be expressed as % change across sleep in maze CT compared to baseline CT before sleep. We have chosen a maze over a word-pair test^{105;235;236} because: 1) it taxes the hippocampus (more than a word-pair tasks would); 2) it's ecologically relevant to AD (*i.e.* spatial disorientation is one of the early clinical AD-symptoms); and 3) there are equivalent rodent models that lend insight into the underlying electrophysiological mechanisms (*i.e.* sharp-wave ripples, which cannot be captured with surface EEG).

Figure 10. Bird's eye view of virtual maze

PiB PET and MRI scans:

On visit 4, baseline and follow-up subjects will receive a single dose of 11.12 mCi PiB and perform a dynamic 60 min amyloid PiB PET-MR scan 35 min after injection.. The radioactive drug (PiB) shall meet appropriate chemical, pharmaceutical, and radionuclidic standards. The dose will be radioassayed proper to administration to ensure dosimetry data is correct. Further, the mass of the PiB is not expected to produce a pharmacologic response. PET/MR scans will be performed on an integrated 3T PET/MR

CONFIDENTIAL

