linear regression, with rate of change of AD_{PiB}mask as the dependent variable and race as independent, adjusting for the matching factors: age, sex, BMI, education and annual income (block 1); ApoE4 and ABCA7 (block 2); DWML volumes, DKI indices and mPFC volume (block 3); and SWS characteristic (*e.g.* relative SWA) (block 4). Other covariates (*e.g.*, psychosocial) will be included in the final models if significantly different between AAs and whites as indicated by unequal variance t tests. Although we anticipate that relative SWA will be the best predictor of longitudinal change in AD_{PiB}mask, the best fitting model will be then replicated with each of the other SWS characteristics not listed before. On a final step, we will test whether the effect of SWS on amyloid deposition is different (*i.e.*, stronger) among AAs. The model would include AD_{PiB}mask change, the binary indicator of race (AA=1 *vs.* white=0) and SWA as described in H1.2. If the interaction is significant, it will imply that the effect of SWA on amyloid varies as a function of race. The sign of the estimated coefficient for this term would indicate whether SWA has a significantly stronger or weaker effect among AA. Exploratory Hypothesis: cognitive z-score change in subjects that show improvement in maze CT will be compared with those that don't show improvement using ANCOVA controlling for age, sex, BMI, race, education and ApoE4 status.

- **Post-hoc analyses**: a subset of *post-hoc* analyses will be performed by controlling by PiB levels at baseline and by splitting the sample into PiB+ and PiB- at baseline and performing a separate analysis for each subset. Stratified analyses will also be performed for men and women, as well as for AAs and whites. In addition, we will formally test the impact of PiB status (defined as PiB SUVR \geq 1.4) on the association of sleep measures with longitudinal increases in AD_{PiB}mask. Although we do not anticipate that sleep or SWS characteristics will change over the follow-up period, *post-hoc* analyses will be performed by assessing longitudinal changes in the sleep measures as correlates and predictors of longitudinal changes in the outcomes measures, using paired sample t-tests to assess the change in outcomes and sleep.

10 Source Documents and Access to Source Data/Documents

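### Maze version switches between baseline and follow-up, but no planned model has a maze-order or maze-version term, so any maze difference costs precision in one Aim 3 outcome and slightly blurs one exploratory grouping

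*Combined protocol and SAP*

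**What the plan says.** Section 6.1 (Sleep-dependent Neuropsychological Tests) states: "Subjects will experience two different mazes at baseline and at the 2.5-year follow-up". Section 5.2 lists one training and one testing session around the second polysomnography night at each time point, so I read this as one maze per time point. On order, section 6.1 says only that "mazes will be counterbalanced across subjects for which maze is experienced first". It does not say how order is assigned or whether this is done within race.

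On comparability: "Both mazes have been designed such that optimal CT is equivalent assuming perfect knowledge of the maze layout". On the score: "Maze performance will be expressed as % change across sleep in maze CT compared to baseline CT before sleep".

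The maze is used in two places:

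- **Hypothesis 3.1 (section 9.1):** "race will be associated with longitudinal changes in global cognition, memory, executive function and sleep-dependent spatial navigational memory". Hypothesis 3.2 asks whether slow wave activity partly explains that association.
- **Exploratory hypothesis (section 9.3):** participants whose maze time improved at baseline are compared with those whose time did not, on later cognitive z-score change, by "ANCOVA controlling for age, sex, BMI, race, education and ApoE4 status".

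The section 9.3 blocks for Hypotheses 2 and 3 cover the matching factors, two genes, imaging measures and a slow-wave-sleep characteristic. Neither they nor the ANCOVA includes maze order or version. The Study Enrollment text in section 4 says "Self-identified AA and whites will be balanced by sex, age, BMI, income and education"; maze order is not among those factors.

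**The concern.** Equal optimal times with perfect knowledge of the layout show that the two mazes have the same floor. They do not show that the mazes are equally easy to learn in one evening or yield the same overnight gain. Participants are trained shortly before sleep and are not at the floor. Expressing the score relative to pre-sleep time does not settle the matter, because pre-sleep time also depends on how hard the layout is to learn.

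If the expected overnight gain differs by D between mazes, the follow-up-minus-baseline change moves by +D in one order and by -D in the other. Counterbalancing cancels this in the overall mean. It leaves the spread in the individual scores, and a model without an order term treats that spread as noise. In the exploratory analysis, whether someone counts as an improver depends partly on which maze came first.

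**Working it through.** **Nearest stated figure.** Section 9.2 gives 80% power for a predictor explaining 3% of variance in Aims 2 and 3, with covariates explaining 25% and complete data on 200. With f² = 0.03/(1 - 0.25 - 0.03) = 0.0417, n = 200 and two-sided alpha 0.05, the noncentral F gives 0.819, so the figure reproduces. It leaves little slack. The plan gives no figure for maze difficulty or order.

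**Inputs.** Group sizes of 150 and 60 and alpha 0.05 are from sections 9.2 and 9.3. The maze difference D is my assumption, from 0 to 0.8. It is in SD of the within-order change score for the race contrast, and in SD of the baseline score for the improver split.

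**Race contrast without an order term.**

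- Variance of the change score: 1 + D².
- Difference detectable with 80% power if D = 0: (1.960 + 0.842) × sqrt(1/150 + 1/60) = 0.428 SD.
- Power at that difference: Φ(2.802/sqrt(1 + D²) - 1.960).

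| D | Variance factor | Power, no order term |
|---|---|---|
| 0 | 1.00 | 80% |
| 0.2 | 1.04 | 78% |
| 0.5 | 1.25 | 71% |
| 0.8 | 1.64 | 59% |

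A simulation (8,000 runs per setting, 105 participants per order overall, not stratified by race) gave power of 0.783, 0.698 and 0.593 at D = 0.2, 0.5 and 0.8. With an order term, power was 0.792, 0.793 and 0.792.

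**Chance imbalance between races.** With 105 per order overall, the central 95% range is 24 to 36 of the 60 white participants on one order. The SD of the race difference in order share is about sqrt(0.25/60 + 0.25/150) = 0.076. The orders differ by 2D, so the contrast can shift by chance by about ±1.96 × 2D × 0.076 = ±0.30D.

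This is not a second cost. The variance of that shift is 4D² × 0.25 × (1/60 + 1/150) = D²(1/60 + 1/150), which is exactly the extra variance in the table. The ordinary standard error already contains it. Simulated type I error without stratification or an order term was 0.051, 0.056 and 0.051.

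**Stratifying by race without an order term.** Power was 0.789, 0.717 and 0.612, with type I error of 0.041, 0.027 and 0.013. The test becomes conservative and little power returns.

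**Exploratory split.** With mean baseline gain 0, the proportion improving is Φ(+D/2) on one maze and Φ(-D/2) on the other: 54% v 46% at D = 0.2, 60% v 40% at 0.5, and 65.5% v 34.5% at 0.8. The outcome compared is cognitive z-score change, which does not use the maze, so the effect is attenuation. Roughly, this is 1/sqrt(1 + D²/4): 0.995 at D = 0.2, 0.97 at 0.5 and 0.93 at 0.8.

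**The case against.** The strongest reply is that no maze difference is documented. The protocol says the mazes were built to be equivalent in optimal time, scores each person against their own pre-sleep time, and describes the task as its own published one. At D = 0.2 the loss is about two points of power, and at D = 0 there is none. This stands, and it is why the point is minor and why the range must include small values.

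It can also be said that section 9.3 does not write out a navigation model. Section 3.1 says Aim 3 follows a similar approach to Aim 2, and section 9.3 admits other covariates that differ significantly between the races, so a marked imbalance in maze order might be picked up. That is only a partial answer. The rule acts on imbalance found in the data, whereas the variance cost arises even when order is perfectly balanced.

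A reader might infer three stronger things that the documents do not support:

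- **That maze difficulty enters every change score.** Global cognition, memory and executive function come from the WHICAP battery (section 6.1), and the primary endpoint is amyloid change. Only the navigation score uses the maze.
- **That the race comparison is biased.** Counterbalancing makes the expected bias zero, provided order is not assigned in a way that tracks race.
- **That order will not be balanced within race.** The text is silent on this; it does not rule it out.

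**Conclusion.** The point holds as one of precision. If the mazes differ in expected overnight gain, omitting maze order adds avoidable variance to one of four Aim 3 outcomes, and omitting baseline maze mildly attenuates one exploratory comparison. No test becomes invalid. The losses grow with D and are small if the mazes are close. They rest on an assumed D, a race contrast not adjusted for other covariates, and complete data on 150 and 60. Because the remedy costs almost nothing, it is worth making without first knowing D.

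**What to change.** In section 9.3, add maze order (A then B, or B then A) as a fixed factor in the navigation-change models for Hypotheses 3.1 and 3.2. Add baseline maze (A or B) as a factor in the exploratory ANCOVA, so that improvers and non-improvers are compared allowing for which maze they did. Keep the stated definition of improvement: centring scores by maze would change it from getting faster overnight to doing better than that maze's average.

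In section 6.1, add a sentence on how order is assigned. Counterbalancing within race is optional and does not replace the order term.

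The cost is a few lines of text and one degree of freedom per model. Maze order has to be known in order to counterbalance it, so no new data are needed. Specifying the term in advance also avoids a later choice about whether to adjust.
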